## **The American British Cowdray Medical Center**

**Date: March 26, 2020**

**NCT05807945**

### **Comparison of Intra-articular 0.2% Ropivacaine vs 0.75% Ropivacaine in Postoperative Knee Arthroscopy**

#### **Abstract:**

All patients with acute lesions assistant to the orthopedic and trauma center of the ABC medical center will be invited to participate in the study. Those that meet the inclusion criteria and later sign an informed consent will be randomized to receive 10 ml of a solution with ropivacaine at 0.75% and 0.2% intraarticular for the first 5 minutes after the end of surgery (closing of surgical wounds). Both the patient, the physician who applies it and the evaluator of outcomes remain blinded to the dose of ropivacaine the patient receives.

Two hours after the end of the surgery, while the patient is in his room, the presence of pain will be evaluated by a visual analog scale (EVA), while the patient is asked to flex and extend his knee. The result will be quantified continuously, to later categorize the pain in none to slight pain (0-3 points) and moderate-severe pain (4-10 points). All the information will be recorded on established forms in the clinical file (general data), that includes the variables of interest for the study, and is reported by the physicians after standardization of all those encharged with collecting information to comply with the conceptual and operative

operationalization of the variables described in the research protocol. In addition to the evaluation of pain, the administration of opiodes to patients for necessary reasons (presence of pain) by the physicians in charge is recorded.

It is hoped that, in patients with knee arthroscopy for acute lesion, there is a difference in the frequency of moderate-severe pain of 30% in the post-operative (frequency of 37.5% in patients with ropivacaine at 2% and frequency of 7.5% in patients with ropivacaine at 7.5%).

## Background

Knee arthroscopy is a minor outpatient orthopedic procedure, used primarily to remove loose bodies, for debridement of meniscal tears, debridement and remodeling of cartilage lesions, ligament reconstruction, meniscus transplants, and arthroscopically assisted synovectomy[1].

Estimates made in the United States of America indicated that in 2006, 6.3 million orthopedic surgical procedures were performed in an outpatient context[1], of which 984,999 (95% CI: 895,999 to 1,073,215) corresponded to knee arthroscopies[1 ]. In Sweden it is estimated that a team consisting of an average of 7 surgeons (from teaching, general and local hospitals) performs 330 (110-2,600) arthroscopies annually[2].

Post-surgical pain after performing knee arthroscopies has been described in 62.5% of patients acutely (4 days after the operation), and in 76.9% of subjects chronically (1 year after surgery)[3]. In patients with moderate-severe preoperative pain (4-10 points according to the visual analogue scale (VAS)), the presence of acute and chronic pain occurs in 45.6% and 42.7%, respectively, while in those with pain between 0 -3 points, acute and chronic pain occurred in 17.2% and 6.9%, respectively[3].

Global Surgical Recovery has been investigated using the Global Surgical Recovery Index after knee arthroscopy, the evaluation tool consisted of a question “Yes, 100% recovery means that your health “You have returned to the same level you had before the surgery, what percentage of recovery do you have now?” (“if 100% recovery means your health is back to the same level as it was before the surgery, what percentage of recovery are you now?”), with 88.5% of participants responding with values  $\leq 80\%$  in a period of 4 days after surgery and 50.0% values  $\leq 80\%$  one year after surgery[3].

Currently there is no guideline or consensus for the treatment of elective knee arthroscopies[2], [4]. However, when analyzing the responses of a questionnaire sent to various orthopedic units members of the “Swedish Arthroscopy Society”, it was reported that the most common anesthesia technique corresponded to 1) general (83%), 2) local anesthesia without or with minimal sedation was used in 13% of patients, 3) while spinal anesthesia was performed in 4% of patients[2]. In the postoperative period, 1/37 (2.70%) of the units interviewed did not use local intra-articular anesthesia for the treatment of pain, 8/37 (21.62%) used short-term lidocaine or prilocaine (with or without adrenaline), in 20

/37 (54.05%) used long-acting intra-articular bupivacaine, 5/37 (13.51%) used morphine and 3/37 (8.10%) NSAIDs[2].

After the use of the different anesthesia methods, the adverse effect on the articular cartilage has been evaluated, in addition to the favorable analgesia effects for pain management, showing no difference in the harmful effect between the use of general, spinal and analgesia. local[5].

The effect of the use of various analgesics on pain control in procedures similar to knee arthroscopy has previously been studied[6-10].

After arthroscopy that does not include a procedure such as anterior cruciate ligament, tibial tuberosity osteotomy, medial patellofemoral ligament or meniscus surgery, a median opioid consumption corresponding to 11.3 (0-52) pills has been reported[11].

### **Acute pain (Outcome)**

Pain has been defined as an unpleasant emotional experience associated with tissue damage, not just a primary sensation; and like any emotional experience, it is subjective[12], [13]. Only the patient himself knows his pain and how much it hurts, therefore any assessment of pain must include the report of the subject suffering from the pain [13]. The evaluation of acute pain, being a time-limited, unidimensional and short event, is easier to measure, is easily reproducible and is not significantly affected by other variables[13].

It is not possible to extrapolate experimentally produced pain to situations where the pain is caused by a pathological process in the patient, because the patient's psychological state, associated with the pathology, is present[13].

### **Pain assessment**

Subjective measurement is the most frequently used way to measure pain; Unidimensional methods only assess intensity and treat pain as a single or simple dimension[13].

In order to standardize the evaluation of outcomes of experimental studies and the choice of optimal measurement instruments within different contexts of clinical epidemiology, initiatives have emerged, such as the COMET initiative[14], from the English “Core

Outcome Measures in Effectiveness Trials". " and COSMIN (COnsensus-based Standards for the selection of health Measurement INstruments)[15]. After a search to identify the best tool for the evaluation of pain in the present study in the different bases of the standardization initiatives for evaluating outcomes, first in the database of the COMET initiative[16], no results were seen. of valid measurement instruments when performing a general search with the terms "Pain" and Knee (knee), or when searching for the terms "Anesthesia and pain control"[17]. However, in the COSMIN initiative's database of measurement instruments for patient-reported outcomes, a search with the term "knee" (Patient-reported outcome measures for the knee)[18] returned a search result, which describes measurement properties of various instruments used in patients with various knee procedures or conditions[19], including the VAS.

### **Visual analogue scale**

The visual analogue scale (VAS) was described and devised in 1976. It consists of a 10 cm line that continuously represents the pain spectrum[13]. The line can be displayed horizontally or vertically, with right-angled endings at the ends, where the descriptions "No pain" and "The worst pain imaginable" appear (Figure 1) [13]. The patient is free to indicate the intensity of his or her pain sensation on the continuous line, which constitutes the main advantage of the measurement method[13]. In the evaluation of patellofemoral pain, the reliability of the VAS is 0.95-0.96, measuring the ability to identify the change in pain intensity in various periods of time (test-retest)[19].

**Figure 1. EVisual Analogue Scale (VAS)**

### **Ropivacaine**

Ropivacaine is a long-acting amide local anesthetic that began clinical use in 1996.[20] Structurally, it is chemically similar to bupivacaine and mepivacaine, because they are derivatives of "pipecoloxylidide" (name not defined in Spanish), however, ropivacaine,

being the agent with the lowest lipophilic behavior of its peers, is characterized by lower toxicity. systemic when compared with bupivacaine and levobupivacaine[21]–[23].

The possible benefits of ropivacaine have been studied in different contexts: 1) in infiltration anesthesia[20], 2) in peripheral neural blockade (sciatic and femoral nerves)[24], [25]; 3)continuous postoperative analgesia[26]–[29]; 4) intra-articular application[30], [31].

Until now, the efficacy (comparison against placebo or non-active substance) of ropivacaine in the control of pain after knee arthroscopy has not been evaluated. However, the results of the efficacy or efficiency of active substances similar to ropivacaine have been studies [32-41]. Ropivacaine, such as bupivacaine or levobupivacaine in pain control, in different strata of the population that has undergone knee arthroscopy, as well as the adverse effects and limitations of studies previously carried out in the population of interest for this study.

### **Research question**

What is the analgesic effect of the intra-articular administration of 0.2% ropivacaine vs 0.75% ropivacaine in the immediate postoperative period of knee arthroscopy in acute injuries?

### **Justification**

The prevalence of moderate-severe pain in post-knee arthroscopy patients is 71.2%. The prevalence of acute postoperative pain is 37.5% and chronic pain is 37.7%, exceeding the prevalence compared to that of other surgical procedures of different specialties.

This study will provide evidence regarding the effect of an anesthetic on postoperative pain control, as well as the effects on reducing opioid consumption and patient mobilization.

The administration of opioids is part of a common practice in pain management, however it represents a risk for patients due to their adverse effects and high risk of dependence. It is necessary to look for alternatives that reduce opioid consumption in postoperative patients, taking care of the cost-benefit for the patient as well as for health institutions.

The reduction in postoperative pain with the applied strategies that has been observed is up to 30% in the immediate postoperative (1st measurement), 20% at 8 hrs (2nd measurement) and 10% at 24% (3rd measurement).

## **Objectives**

General objective:

- To evaluate the analgesic effect of the intra-articular administration of 0.75% ropivacaine in the immediate postoperative period of knee arthroscopy in acute injuries.

Specific objectives:

- To evaluate the effect of intra-articular administration of 0.75% ropivacaine in reducing opioid consumption in the immediate postoperative period of knee arthroscopy in acute injuries.
- To evaluate the effect of intra-articular administration of 7.5% ropivacaine on mobility in the immediate postoperative period of knee arthroscopy in acute injuries.

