### *Sample size*

Expecting an absolute difference, an absolute difference of 30% is expected for the presence of moderate-severe pain, considering a level of significance=5% and power=80%. Needed are 68 subjects, 34 for each arm.

Given that the evaluation of outcome is performed 2 hrs. after the application of the maneuver, and due to the low incidence of postoperative anesthetic complications, loss of information is estimated at <1%.

*Sample size and statistical analysis:* Sample size was estimated to establish a difference of 30% in considering the presence of moderate-severe pain among patients treated with different doses of ropivacaine, considering an alpha level of 0.05 and beta of 0.20. Required

were 68 patients divided into two groups of 34 each. Loss of information was expected at <1%, and 2 subjects were added to the sample size, increasing the requirement to 70 subjects in total. For statistical analysis, the statistical program SPSS version 27 will be used (IBM Armonk, New York). Contrast of the incidence of outcomes between the two groups by different doses of ropivacaine will be carried out by  $\chi^2$  or Fisher exact test, when necessary. Multivariate analyses will be performed by logistic regression analysis, considering a value of  $p < 0.05$  as significant, and double gradient differences in exposure to different variables between treatment groups were included in multivariate analysis.

In the *intention-to-treat analysis* (ITT), the main and secondary outcomes will be contrasted between the groups, considering the randomization of the different doses of ropivacaine, and in the *per-protocol analysis (PP)*, the results of the incidence of moderate-severe pain will be contrasted between groups formed by randomization; however, those that received opioids in the first 2 hours post-surgery will be excluded, in order to know the effect of the use of ropivacaine at 7.5% without the effect of a conjugate maneuver.

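### Do the four mentions of ropivacaine at 7.5% or 2% call for a change to the statistical plan?

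*Combined protocol and SAP*

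**What the plan says.** The title is "Comparison of Intra-articular 0.2% Ropivacaine vs 0.75% Ropivacaine in Postoperative Knee Arthroscopy". The same pair of strengths, or one member of it, appears in the Abstract's description of the intervention, the Research question, the general and opioid objectives, the Hypothesis, the Maneuver section and the independent-variable entries under Variables to be evaluated.

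Three places depart from this:

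- **Objectives, mobility:** "To evaluate the effect of intra-articular administration of 7.5% ropivacaine on mobility in the immediate postoperative period of knee arthroscopy".
- **Abstract, expected result:** "frequency of 37.5% in patients with ropivacaine at 2% and frequency of 7.5% in patients with ropivacaine at 7.5" (the last figure carries a percent sign in the text). Here 37.5% and the first 7.5% are pain frequencies; 2% and the second 7.5% are strengths.
- **Sample size section, purpose of the per-protocol analysis:** "the effect of the use of ropivacaine at 7.5% without the effect of a conjugate maneuver".

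The rest of the Sample size section refers to the doses without figures. The sample-size sentence has "among patients treated with different doses of ropivacaine", the main comparison is a "Contrast of the incidence of outcomes between the two groups by different doses of ropivacaine", and the intention-to-treat analysis is made "considering the randomization of the different doses of ropivacaine".

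**The concern.** Strength is the only planned difference between the arms: the Blinding and Exit from the study sections fix the volume at 10 ml and make the preparations look alike. A document that states its one experimental variable in two ways, a factor of ten apart, deserves a check.

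The locations add to the worry. One is a formal objective. One is the only sentence that gives arm-specific planning rates. The third is in the analysis text, where 7.5% is the only strength named at all. If the analysis were tied to those labels, the mobility objective and the per-protocol result would refer to a strength that neither arm is defined to receive. A report worded from the Sample size section alone could repeat the mismatch. Had the planning rates belonged to a different pair of treatments, the basis of the sample size would also be open to question.

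**Working it through.** **1. Count of the strength mentions**

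| Place | 0.75% | 0.2% | 7.5% | 2% |
|---|---|---|---|---|
| Title | 1 | 1 | – | – |
| Abstract | 1 | 1 | 1 | 1 |
| Research question | 1 | 1 | – | – |
| Objectives | 2 | – | 1 | – |
| Hypothesis | 1 | – | – | – |
| Maneuver | 1 | 1 | – | – |
| Sample size section | – | – | 1 | – |
| Variables to be evaluated | 2 | 2 | – | – |
| Total | 9 | 6 | 3 | 1 |

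The total is 9 + 6 + 3 + 1 = 19, of which 3 + 1 = 4 deviate (4/19 = 21%). The expected pain frequency of 7.5% in the Abstract is an event rate and is not counted.

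**2. Pattern of the deviation**

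7.5/0.75 = 10 and 2/0.2 = 10, so each shift is exactly tenfold. The ratio between arms is 0.75/0.2 = 3.75 in one notation and 7.5/2 = 3.75 in the other, so the stronger arm is the same arm in both. The Abstract gives the lower pain rate to the stronger arm, which agrees in direction with the Hypothesis.

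**3. Does the sample size depend on the strength?**

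Inputs: p1 = 0.375 and p2 = 0.075 (Abstract); significance level 0.05, power 80% and 34 per arm (Sample size section). The documents do not state sidedness; two-sided is assumed. The planned difference is 37.5 − 7.5 = 30 points, the absolute difference given in the Sample size section.

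Exact power of Fisher's test with n per arm is the sum, over all event counts a and b with a two-sided Fisher p below 0.05, of Bin(a; n, 0.375) × Bin(b; n, 0.075).

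- n = 33: 79.4%
- n = 34: 81.0%

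Within the range checked (29 to 35), 34 is the smallest n that reaches 80%, so the plan's figure is reproduced. The pooled normal formula without continuity correction gives 30 per arm, so the stated 34 also covers that version. Strength does not appear in either calculation; relabelling the arms leaves 34 per arm, 68 in total, and 70 with the two added subjects.

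**4. Do the comparisons depend on the strength?**

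- **Main and secondary outcomes, intention to treat:** compared according to randomisation.
- **Per-protocol:** results "will be contrasted between groups formed by randomization", leaving out those given opioids in the first 2 hours. The 7.5% is only in the clause that says why; the rule for who is analysed contains no strength.
- **Mobility:** recorded as present or absent after the patient is asked to move the leg. The definition names no strength.

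**5. Do the places that direct administration agree?**

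The Abstract's intervention sentence, the Maneuver section and both operational definitions give the same two strengths in 10 ml. None of the four deviating mentions instructs anyone to prepare or give a dose.

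**The case for a change.** The strongest case for acting is that this is more than one stray character. The shift recurs in three sections and affects the labels of both arms in the Abstract. In a 10 ml volume, reading percent as grams per 100 ml, the labels correspond to 20 mg against 200 mg and 75 mg against 750 mg. No passage explains a notation that would make the two sets agree, and contradictory text in an objective and in the analysis section should not be left standing.

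The textual part of this stands: the passages contradict one another and must be reconciled. The documents leave the choice of figures to the sponsor, and nothing here decides it.

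The step to a flaw in the plan does not stand. To mislabel the per-protocol result, an author would have to ignore the title, the Maneuver section and the variable table and take the arm name from a purpose clause. The regular factor of ten also suggests a notation slip: 0.2% weight per volume is 2 mg/ml and 0.75% is 7.5 mg/ml, so the deviating figures are the mg/ml values of the defined arms with a percent sign attached. The documents never use mg/ml, so that is inference, and the conclusion does not need it.

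Two limits apply to the evidence on this side. The comparisons in the Sample size section name no strength, so they can only be said not to conflict with the arm definitions. The Hypothesis speaks of a 30% reduction without saying that it is absolute, so it supports the direction of the planning rates and not the 30-point size.

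**Conclusion.** The concern describes the text correctly but calls for no change to the plan. Four of 19 mentions, in three sections, are clerical deviations to be reconciled in the wording. The effect on arms, endpoint, test, comparisons and sample size is nil: 34 per arm holds whichever label is used, and the analysis sets are defined by randomised group and, for the per-protocol set, by opioid use. An analyst would label the arms from the allocation and the variable definitions and reach the same tables.

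This rests on two assumptions: that the Maneuver section and the variable definitions, which agree with each other, are what define the randomised arms for analysis; and that the test is two-sided, which the documents do not state but which reproduces the stated number. It is not a judgement on which strength is clinically right.

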## **Hypothesis**

The Intraarticular administration of 0.75% ropivacaine reduces acute pain by 30% in postoperative knee arthroscopy patients in acute injuries.

## **Methods**

All patients with acute knee articular cartilage lesions who attend the Orthopaedic and Trauma Center of the ABC Medical Center will be invited to participate, under the scrutiny of a sole surgical team.

### *Selection criteria*

- Mental health: healthy (not taking any medication)
- Articular cartilage lesion Grade I, II or III by Outerbridge
- Elective knee surgery
- Patients with any of the following diagnoses:
- Simple menisc lesion

-Lesion of a single knee (unilateral)

*Exclusion criteria*

- Neuromotor diseases (alterations in step, strength or sensitivity)
- History of knee surgery (orthopedic)
- Instability that includes knee ligament lesions
- Addictions
- Mental diseases in medical treatment
- Hepatic diseases
- Allergy to any of the medications used in the study
- Epidural or peridural anesthesia
- Chronic pain in treatment
- Postoperative drain of knee arthroscopy
- Pregnant or lactating

*Model description*

After confirming that the patients meet the selection criteria, they will be invited to participate in the study. Upon accepting through signed informed consent, the physician in charge of randomization (physician 1) will be informed and the surgery scheduled. The day of the surgery, the physician in charge of randomization will report the maneuver to be received from the anesthesiologist (physician 2) in charge, who will prepare the dose of ropivacaine and give it to a physician blinded to the maneuver (physician 3); this physician will apply the ropivacaine intraarticular to the patient. The level of pain will be evaluated two hours after the end of surgery by a physician blinded to the maneuver the patient has received (physician 4), while the patient is in his room, and the presence of acute-moderate-severe pain (4-10 points) is evaluated by a visual analog scale (EVA) while the patient is requested to flex and extend the knee.

*Randomization:*

Randomization will be performed by number generator software OxMaR (Oxford Minimization and Randomization).

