#### *Variables to be evaluated*

Dependent variable	
Pain (Primary outcome)	Conceptual definition: Sensory and emotional experience associated with a present or potential injury or a described one.  Operational definition: The sensation of painful discomfort at the surgical site (Mild, moderate or severe).  Type of variable: Dichotomous qualitative.  Measuring instrument: VAS (0-10 points)  Measurement units: Mild 0-3 points, moderate-severe 4-10 points.

Opioid use	
Conceptual definition: Drug whose analgesic action is produced thanks to the interaction with the opioid receptors of the neurons of the central nervous system.
 
Operational definition: According to the VAS pain score administration of Tradol dose of 50mg IV.
 
Type of variable: Qualitative dichotomous
 
Measuring instrument: Information extracted from the patient's file.
 
Measurement units: Not use / Use.

Mobility	
Conceptual definition: Amplitude of joint oscillation within natural limits.
 
Operational definition: The active mobility performed by the patient in the postoperative period.
 
Variable type: Dichotomous qualitative.
 
Measuring instrument: Observation made by the doctor in the postoperative period after the indication of flexion and extension of the leg, elevation and descent of it actively before the doctor.
 
Measurement units: Present / absent.

Independent variable	
Ropivacaine 0.75%	
Conceptual definition: Long-lasting amide-type local anesthetic with lower lipid solubility.
 
Operational definition: IA administration to the knee of 10 ml of 0.75% ropivacaine.
 
Variable type: Dichotomous qualitative.
 
Measuring instrument: Experimental maneuver.

	Measurement units: No / Yes
Ropivacaine 0.2%	
Conceptual definition: Long-acting amide-type local anesthetic with lower lipid solubility
 
Operational definition: IA administration to the knee of 10 ml of 0.2% ropivacaine.
 
Variable type: Dichotomous qualitative.
 
Measuring instrument: Experimental maneuver.
 
Measurement units: No / Yes

Peripheral variables/covariates/Probable confounders /Probable interactors	

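### Mobility is defined as amplitude but recorded only as present or absent, and the primary VAS is taken on a requested movement with no resting score and no record of whether the movement was done

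*Combined protocol and SAP*

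**What the plan says.** **Mobility.** The Objectives section has a specific objective to evaluate the effect of the higher concentration "on mobility in the immediate postoperative period of knee arthroscopy in acute injuries". The table under Variables to be evaluated gives the concept as "Amplitude of joint oscillation within natural limits". The instrument is "Observation made by the doctor in the postoperative period after the indication of flexion and extension of the leg, elevation and descent of it actively", and the units are "Present / absent". No degree threshold, grading or clock time is given. No expected rate, effect size or power is given for mobility.

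**Primary pain score.** The model description in Methods fixes the assessment at two hours after surgery, by a blinded physician. There, pain "is evaluated by a visual analog scale (EVA) while the patient is requested to flex and extend the knee". The Abstract agrees: the score is taken "while the patient is asked to flex and extend his knee", and the plan is then "to later categorize the pain in none to slight pain (0-3 points) and moderate-severe pain (4-10 points"). The variables table defines pain as "The sensation of painful discomfort at the surgical site (Mild, moderate or severe") and mentions neither rest nor movement. No resting score is planned, no range or number of repetitions is set, and nothing says how to handle a patient who stops early or declines to move.

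**The concern.** There are two linked measurement gaps.

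1. The mobility scale cannot measure the plan's own construct. A knee that moves a little and a knee that moves through its full range can both be coded present, so a between-arm difference in range leaves no trace in the data. The item also joins two tasks under one code: a patient who flexes and extends but cannot raise the leg, or the reverse, has no defined value. Two observers could code that patient differently.

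2. The stimulus for the primary score is left partly to the patient. A mark of 2 from someone who kept the knee still and a mark of 2 from someone who moved it fully are both coded as none to slight pain, and no planned field separates them. With 34 per arm, the plan expects 34 × 0.375 = 12.75 events against 34 × 0.075 = 2.55, so a few ambiguous scores could matter.

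**Working it through.** **Inputs from the plan.** Moderate-severe pain 37.5% vs 7.5% (Abstract); 34 per arm, alpha 0.05, power 80%, chi-squared or Fisher exact test (Sample size). Sidedness is not stated; two-sided is assumed.

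**1. The plan's own figure.** Exact enumeration of Fisher power at 37.5% vs 7.5% gives 79.4% at 33 per arm and 81.0% at 34. So 34 is the first size that reaches 80% under Fisher, and the stated sample size reproduces. Chi-squared power at 34 is 88.5%.

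**2. Mobility: degrees against present/absent.** Assumptions: active range is roughly normal with equal SD, the arms differ by 0.7 SD, and present means range above some cut.

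- *In degrees (two-sample t test).* Noncentrality = 0.7 × √(34/2) = 0.7 × 4.123 = 2.886; df = 66; critical value 1.997. Power is 81.2%.
- *Binary.* If a share p₁ is present in the worse arm, the better arm has p₂ = Φ(Φ⁻¹(p₁) + 0.7). For p₁ = 90%: Φ(1.282 + 0.7) = Φ(1.982) = 97.6%. For p₁ = 80%: Φ(0.842 + 0.7) = Φ(1.542) = 93.8%. For p₁ = 50%: Φ(0.7) = 75.8%.

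Exact power at 34 per arm:

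| Present, worse vs better arm | Fisher throughout | Chi-squared, Fisher if an expected count is below 5 |
|---|---|---|
| 90% vs 97.6% | 5.9% | 6.1% |
| 80% vs 93.8% | 25.3% | 30.9% |
| 50% vs 75.8% | 52.3% | 62.2% |

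The trigger of 5 is an assumption, since the plan does not say when Fisher applies. On the same shift, even an even split in the worse arm falls short of the 81% available in degrees.

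**3. Primary score: an illustration only.** Suppose a share g of patients with truly moderate-severe pain avoid the movement and mark 0-3. The documents give no g. Both rates become (1 − g) times the planned value:

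| g, both arms | Rates | Difference | Fisher | Chi-squared | Chi-squared, Fisher if an expected count is below 5 |
|---|---|---|---|---|---|
| 0 | 37.5% vs 7.5% | 30 points | 81.0% | 88.5% | 88.0% |
| 10% | 33.8% vs 6.8% | 27 points | 74.5% | 83.8% | 82.3% |
| 20% | 30.0% vs 6.0% | 24 points | 66.4% | 78.0% | 74.4% |
| 30% | 26.3% vs 5.3% | 21 points | 56.5% | 71.4% | 63.9% |

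If it happens only in the 0.2% arm, Fisher power is 70.6%, 57.6% and 43.1% at 10%, 20% and 30%. At 20% in that arm, 12.75 × 0.2 = 2.55 patients would be recoded. This shows what the missing fields could hide. It does not estimate what will happen.

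**The case against.** - **An able/unable item is a legitimate outcome.** That stands in general, and the documents give no mobility rate. If the item split the arms 62.5% vs 92.5%, Fisher power would be 81%. On the scale used above, that split needs a shift of 1.440 − 0.319 = 1.12 SD. The item is weak only if most patients can move at all, but whatever the rate, it does not measure amplitude.
- **A reader might infer that mobility is present by construction for anyone with a pain score, and so carries almost no information.** The documents do not support this. Movement is requested, not required, so a patient who refuses can have both a VAS and mobility absent. Mobility also includes leg raising and has no clock time, so a single joint assessment is not documented. The binary item may even identify outright refusers. It would miss those who stop early, and no analysis links it to the VAS.
- **A reader might infer that the primary comparison is biased because guarding is rewarded.** That is conjecture. A patient who stops because it hurts has just felt pain on movement and may well mark 4 or more. No guarding rate is given. The Justification section cites 37.5% as a prevalence of acute postoperative pain; if that was an observed rate, some under-reporting may already be in it. Under chi-squared, g = 10% in both arms still leaves power above 80%. Opioid use is recorded too, though as a dose given according to the same VAS it is only a partial check.
- **Counting inability to move as a primary event would be a debatable change of endpoint.** This stands. The sample size rests on rates for moderate-severe pain alone, and a composite would need new ones.

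**Conclusion.** The point holds as a measurement gap. It does not show a biased primary result. Two facts rest on the text alone: mobility is defined as amplitude but has no amplitude measure, threshold, time or code for a patient who does one task only; and the primary VAS has no resting counterpart and no record of whether the requested movement took place.

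The size is conditional. Under an assumed 0.7 SD shift at 34 per arm, degrees give about 81% power, against about 6% for the binary item with 90% present in the worse arm, and 25-31% with 80% present. The shift, the normal shape and these rates are all assumptions. For the primary score, the frequency of low scores without movement is unknown, and the planned data could not reveal it. The sample size of 34 per arm is not in question.

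**What to change.** **Variables to be evaluated (mobility).** Record active knee flexion and extension in degrees at the 2-hour assessment, by the same blinded physician who scores pain. Record leg raise as a separate yes/no item. Compare range between arms, naming one summary in advance (for example, the total active arc).

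**Methods, model description (pain).** Take a resting VAS immediately before the movement. Record whether the movement was completed and, if not, whether pain was the reason. State in the variables table that the primary VAS is the one taken on movement.

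**Analysis.** Keep the primary event as VAS 4-10, so that the 37.5% vs 7.5% assumptions and the sample size stand. Report VAS 4-10 or unable to move because of pain as a sensitivity analysis.

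**Cost.** A goniometer reading and a few form fields, about a minute per patient, at the same visit and with the same staff. Treatment and sample size do not change.
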